### 5.2 EXCLUSION CRITERIA

Participants who meet any of the following exclusion criteria will not be eligible for participation in this study:

1. The participant has received any investigational compound within 90 days before dosing.
2. The participant is an immediate family member, CRU employee, or is in a dependent relationship with a CRU employee who is involved in the conduct of this study (eg, spouse, parent, child, sibling) or may consent under duress.

3. The participant has any clinically significant illness, such as cardiovascular, neurologic, pulmonary, hepatic, renal, metabolic, gastrointestinal, urologic, immunologic, endocrine, or psychiatric disease or disorder, or other abnormality, which may affect the participant's safety, increase risk of seizure or lower the seizure threshold, or potentially confound the study results. It is the responsibility of the Investigator to assess the clinical significance of any conditions the participant may have; however, consultation with the Xentria Medical Monitor may be warranted.
4. The participant has a known hypersensitivity to any component of the formulation of XTMAB-16.
5. The participant has a positive result for drugs of abuse (defined as any illicit drug use) or alcohol at Screening or Baseline (Day -2).
6. The participant has a history of drug abuse (defined as any illicit drug use) or a history of alcohol abuse within 1 year prior to Screening or is unwilling to agree to abstain from alcohol and drugs throughout the study.
7. The participant has taken any excluded medication, supplements, or food products during the time periods listed in [Table 4](#).
8. If female, the participant is pregnant or lactating or intends to become pregnant before, during, or within 90 days after the last dose of study drug or intending to donate ova during such time period.
9. If male, the participant intends to donate sperm during the study or within 90 days after the last dose of study drug.
10. The participant has a history of autoimmune disease or respiratory disorders.
11. The participant or any immediate family member has a history of cancer, except basal cell carcinoma, that has not been in remission for at least 5 years prior to Baseline (Day -2).
12. The participant has a condition that can potentially reduce drug clearance (eg, renal or hepatic insufficiency).
  - a. Glomerular filtration rate <60
  - b. ALT >41 U/L
  - c. AST > 34 U/L
  - d. Alkaline phosphatase >117 U/L
  - e. Total protein >8.2 g/dL

### 5.3 LIFESTYLE CONSIDERATIONS

From Day -2 and throughout the study duration, participants should refrain from excessive use of alcohol, tea, coffee, chocolate, quinine, or caffeine-containing beverages.

Participants will be requested to follow a stable lifestyle with no intensive physical activity from Day -2 through the end of study (EOS) visit.

During the confinement, standardized breakfast when applicable, lunch, and dinner will be given as scheduled by the CRU, with every participant on the same meal schedule. There will be no water restrictions for participants; water supply will be at least 1500 mL for each 24-hour period. During the confinement period (Day -2 to Day 8), participants will be given a menu for the dosing period that includes 3 meals and an evening snack, not to exceed 30% fat (relative to the total calories). The meals served on the PK assessment days should be identical for each cohort in the study. The study menu should be recorded and submitted to the study file with a copy provided to the Sponsor prior to the start of the study. Whether the meal was fully consumed, or not, will be recorded.

If a blood draw or any study procedure coincides with a meal, the blood draw will take precedence followed by the study procedure and then the meal.

XTMAB-16 and placebo will be administered on Day 1 in same manner for each cohort (pre- or post-meal). Participants may consume water ad libitum following dosing.

Vital signs will be collected in a supine position except for during the infusion, when the procedures will be performed in a semi-supine/semi-reclined position (see Section 8.2.3). Infusion will occur in a semi-supine/semi-reclined position. After dosing, the participant will be observed by staff for up to 2 hours—at the Investigator's discretion for up to 4 hours, if necessary – except as necessitated by the occurrence of an AE or study procedures (eg, obtaining 12-lead ECG).

Participants will be immunocompromised by administration of study treatment and should be instructed to quarantine at home for 6 days after discharge from the study unit.

#### 5.4 SCREEN FAILURES

Screen failures are defined as participants who consent to participate in the clinical trial but are not subsequently randomly assigned to the study intervention or entered in the study. A minimal set of screen failure information is required to ensure transparent reporting of screen failure participants, to meet the Consolidated Standards of Reporting Trials (CONSORT) publishing requirements and to respond to queries from regulatory authorities. Minimal information includes demography, screen failure details, eligibility criteria, and any SAE.

Individuals who do not meet the criteria for participation in this trial (screen failure) because of a nonclinically significant laboratory abnormality may be rescreened once at the discretion of the Investigator. Rescreened participants should be assigned the same participant number as for the initial screening; those who fail the drug test may not be rescreened.

#### 5.5 REPLACEMENT OF PARTICIPANTS

- Participants who sign the informed consent form and are randomized but do not receive the study intervention may be replaced.

- Participants who sign the informed consent form, are randomly assigned to treatment, receive the study intervention, and subsequently withdraw or are withdrawn or discontinued from the study before Week 2, will be replaced.
- Participants who are lost-to-follow-up will be replaced.

Replacement participants will be assigned to the same treatment assignment as the participant who discontinued.

## 6 STUDY INTERVENTION

## 6.1 STUDY DRUG ADMINISTRATION

### 6.1.1 STUDY DRUG DESCRIPTION

Characterization studies were performed on XTMAB-16 drug substance batches produced in the commercial scale. Results include testing of chemical, physical, and biological properties to establish specifications in terms of identity, purity, and biological activity by a panel of orthogonal assays.

Nonclinical studies of in-vitro biological activity of XTMAB-16 have been performed, including a potency assay, ligand binding assays to TNF $\alpha$ , tissue cross-reactivity, antibody-dependent cellular cytotoxicity, and complement-dependent cytotoxicity activity, and binding to Fc receptors. Please refer to the IB for details.

## 6.1.2 DOSING AND ADMINISTRATION

XTMAB-16 or placebo will be administered once on Day 1 by IV infusion at the required concentration in a volume outlined in the Pharmacy Manual over a period of not less than 2 hours (unless otherwise specified in the Pharmacy Manual). The dose to be administered (0 [placebo], 2, or 4mg/kg) will be determined by the participant's cohort and treatment assignment.

Before XTMAB-16 infusion, the Investigator should carefully read the pretreatment checklist and go over the questions with the participant. Refer to the Administration Guide for the supplies needed, administration instructions, and important information on what to do in the event the participant experiences an infusion reaction.

XTMAB-16 should be administered with an infusion kit and 1.2 micron filter via an infusion pump. See the Pharmacy Manual for details.

## 6.2 PREPARATION/HANDLING/STORAGE/ACCOUNTABILITY

### 6.2.1 ACQUISITION AND ACCOUNTABILITY

The Sponsor will notify the Investigator and pharmacy prior to shipment of drug supplies and other related clinical supplies regarding the anticipated date of their arrival at the pharmacy. Shipment will be sent directly to the delegated personnel at the pharmacy.

All shipped clinical supplies will be appropriately documented to ensure proper handling in case of emergency.

Shipment will be sent under controlled conditions. Each shipment of clinical supplies for the trial will contain a certificate of analysis and a shipment certificate detailing the content of shipment.

Transportation temperature will be monitored and recorded by temperature-monitoring devices. The CRU is required to acknowledge receipt of the study drug and verify the contents, quality, and temperature of the study drug.

Initial clinical supply shipment will be sent automatically upon regulatory and Sponsor approval.

XTMAB-16 must be kept in a secured area with access limited to designated study personnel. Only personnel under the supervision of either the Investigator or the local pharmacist are authorized to handle XTMAB-16.

Refer to the Pharmacy Manual for additional information and details.

### 6.2.2 FORMULATION, APPEARANCE, PACKAGING, AND LABELING

[REDACTED]  
[REDACTED]  
[REDACTED]  
[REDACTED]  
[REDACTED]  
[REDACTED]  
[REDACTED] This information is  
also detailed in the pharmacy manual.

The matching placebo has the same formulation as that the drug product except contains no XTMAB-16. [REDACTED]  
[REDACTED]  
[REDACTED]  
[REDACTED]

The study drug and matching placebo will be packaged and labeled according to the current Good Manufacturing Practice (cGMP) guidelines for drugs used in clinical trials and any other

relevant local regulatory requirements. Details of the packaging and labeling will be found in the Pharmacy Manual provided by the Sponsor and/or delegate.

#### 6.2.3 PRODUCT STORAGE AND STABILITY

XTMAB-16 drug product should be stored at 2°C to 8°C (refrigerate). The clinical supplies storage area at the CRU must be monitored by the CRU staff for temperature consistency with the above instructions. Documentation of temperature monitoring should be maintained at all times until study closure.

Do not use beyond the expiry date provided by the Sponsor.

Upon removal from refrigerated storage, XTMAB-16 cannot be returned to refrigerated storage. XTMAB-16 vials are for single use only. Any unused portion should be placed in quarantine for monitor review. No vials should be discarded without Sponsor approval.

Infusion should begin within 1.5 hours of reconstitution and dilution. The infusion must be administered over a period of not less than 2 hours and must use an infusion set with an inline, sterile, non-pyrogenic, low-protein-binding filter (pore size of 1.2 µm or less). The vials do not contain antibacterial preservatives; therefore, any unused portion of the infusion solution should not be stored for reuse.

The Investigator will be notified of any expiry date or retest date extension of Sponsor-supplied drug during the study conduct. On expiry date notification from the Sponsor or designee, the CRU must complete all instructions outlined in the notification, including segregation of expired Sponsor-supplied drug for destruction.

In the event of expiry date extension of supplies already at the CRU, a memo will be provided by the Sponsor with the retest period and retest date.

#### 6.3 MEASURES TO MINIMIZE BIAS: RANDOMIZATION AND BLINDING

In this study participants will be randomly assigned to treatment (XTMAB-16 or placebo) and treatment assignment will be double-blind: participants and all study staff will be blind to participant treatment assignment for the duration of the study except as specified.

The randomization schedule will be generated by an unblinded statistician (third-party unblinded) and will be provided to the CRU pharmacist prior to the start of this study. All randomization information will be stored in a secured area, accessible only by authorized personnel.

The Investigator (or designee) will assign participant numbers as participants are screened for the study. In accordance with the randomization numbers, the participant will receive the study treatment regimen assigned to the corresponding randomization number.

To maintain the treatment blind, an otherwise uninvolved, third-party unblinded CRU staff member (eg, pharmacist) will be responsible for the preparation and dispensing of all study

treatment according to the randomization schedule and assigned treatment for the individual participant. The unblinded pharmacist will have no contact with study participants and will ensure that no treatment assignment information is transmitted to study unit staff except as defined in Section [6.3.1](#).

---

#### 6.3.1 UNBLINDING PROCEDURE

The study drug blind shall not be broken by the Investigator unless information concerning the treatment assignment is necessary for the medical treatment of the participant. All study assessments and causality should be performed, if possible, prior to unblinding. In the event of a medical emergency, if possible, the Sponsor's Medical Monitor should be contacted before the treatment assignment blind is broken to discuss the need for unblinding.

For unblinding a participant, the treatment assignment blind can be obtained by contacting the dispensing pharmacist. Code break envelopes will be supplied for emergency unblinding when the pharmacist is unavailable.

The Sponsor must be notified as soon as possible if the treatment assignment blind is broken. The date, time, and reason the blind is broken must be recorded in the source documents and the same information (except the time) must be recorded on the electronic case report form (eCRF).

If the blind must be broken for the safety of the participant, the PI and CRO should refer to the Unblinding Plan for instructions and details for review of safety data for that cohort and the impact on dose escalation and/or stopping rules.

If any CRU personnel are unblinded, study drug dosing must be stopped immediately and the participant must be withdrawn from the study.

No change should be made to any assessment of the participant after unblinding.

---

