#### 4.1.1 DOSE ESCALATION

For all cohorts, a sentinel group of 2 participants (1 assigned to XTMAB-16 and 1 assigned to placebo) will be dosed at least 48 hours before the remaining participants in the same cohort. After blinded review of the available safety and laboratory data by the PI, if no notable safety signals are identified, the remaining participants within the same cohort will be dosed.

Participants within a cohort should be dosed at least 1 hour apart.

As XTMAB-16 is a TNF $\alpha$  inhibitor, which have well-characterized clinical safety profiles, it can be given to participants in the 4 mg/kg dose group after 14 to 21 days clinical assessment of the participants at 2 mg/kg dose group, unless safety concerns arise.

Dose escalation will be stopped as soon as safety signals or risks are identified or anticipated, based on:

- Number of abnormal and clinically significant safety laboratory results
- Number of SAEs and/or TEAEs with severity/intensity high enough for a meaningful decision
- Proportion of TEAEs of the same type high enough to justify the decision

The severity rating is adapted to healthy participants, taking into account event characteristics such as type, deleterious potential, occurrence, progression, and monitorability. A solitary SAE occurrence is not by itself a criterion for making a decision (assessment depends on the nature of the reported event). See Section 4.1.2 for details on stopping rules.

A decision to proceed from dose “n” to the next higher “n+1” dose will be made jointly by the Sponsor and the Investigator based on a preliminary Investigator blinded safety report inclusive of the 12 participants in dose level cohort “n”. The relevant data for this decision should be, at a minimum, AEs, liver and kidney function tests, ECG, blood pressure, and heart rate.

For safety purposes, the treatment of a specific participant may be unblinded before the next dose level is administered, after mutual agreement between the Sponsor and the Investigator.

An unscheduled PK sample collection and analysis may be performed to support the clinical safety assessment, if needed in the event of a safety signal of concern.

Depending on the tolerability profile and safety laboratory results observed in the dose level cohort “n,” one of the following decisions will be made for cohort “n+1”:

- Dose escalation may continue as scheduled.

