## 7 STUDY INTERVENTION DISCONTINUATION AND PARTICIPANT DISCONTINUATION/WITHDRAWAL

### 7.1 DISCONTINUATION OF STUDY DRUG

A single dose of study treatment will be administered in this study. Study treatment will only be discontinued if an unforeseen occurrence interrupts or prematurely stops the 2-hr IV infusion. Discontinuation from study treatment does not mean discontinuation from the study, and remaining study procedures should be completed as indicated by the study protocol. If a clinically significant finding is identified (including, but not limited to changes from Baseline) after enrollment, the Investigator or qualified designee will determine if any change in participant management is needed. All events or clinically relevant findings that cause the interruption or premature cessation of dosing will be reported as an AE.

The data to be collected at the time of study treatment interruption or discontinuation will include the following:

- Reason dosing was interrupted/stopped
- Estimate of how much of the study treatment dose was delivered (%)
- How long the participant was observed for safety after the event
- Whether the participant continued in the study or was withdrawn.

Participants who are withdrawn from the study after interruption or premature discontinuation of study treatment dosing should undergo EOS procedures as noted in the SoA (Section 1.3).

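### Section 6.3.1 withdraws a participant from the study when CRU personnel are unblinded, which ends scheduled follow-up for people unblinded because of a medical need

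*Protocol*

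**What the plan says.** Protocol Section 6.3.1 restricts when the investigator may unblind a participant: "The study drug blind shall not be broken by the Investigator unless information concerning the treatment assignment is necessary for the medical treatment of the" […]. It then sets the consequence: "If any CRU personnel are unblinded, study drug dosing must be stopped immediately and the participant must be withdrawn from the study". This covers the study, not only the drug. The same section asks for assessments and causality to be completed before unblinding where possible, forbids changing them afterwards, and has the date and reason recorded on the eCRF.

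Three other protocol sections bear on this:

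- **Section 7.1** notes that "A single dose of study treatment will be administered in this study", and sets the default for stopped drug: "Discontinuation from study treatment does not mean discontinuation from the study, and remaining study procedures should be completed as indicated by the study protocol".
- **Section 7.2** lists two reasons for discontinuing a participant from the study: loss to follow-up and termination by the sponsor. Unblinding is not among them.
- **Section 5.5** replaces a dosed participant who is withdrawn before Week 2, and adds: "Replacement participants will be assigned to the same treatment assignment as the participant who discontinued".

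Unblinding can also arise elsewhere. Section 4.1.1 says "For safety purposes, the treatment of a specific participant may be unblinded before the next dose level is administered", by agreement of sponsor and investigator. Under Section 4.1.2.2 the sponsor breaks the blind when a stopping criterion is met.

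**The concern.** By the protocol's own rule, the investigator breaks the blind because a participant's care requires it. Making that a reason to leave the study ties missing data to the outcome the trial is designed to observe. The single objective covers safety, tolerability, immunogenicity, PK and biomarkers, with visits to Day 71, and Section 9.4.8 allows no imputation. After the infusion there is no dosing left to stop, so the remaining effect of the rule is to end scheduled assessments. With 9 active participants per dose, losing one informative profile matters.

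**Working it through.** **1. Planned follow-up.** The synopsis gives 28 days of screening, 57 of treatment and 14 of follow-up: 28 + 57 + 14 = 99 days, as stated. End of study is Day 57 + 14 = 71, and the last PK hour is 70 × 24 + 2 = 1682, as scheduled. There is no sample-size calculation to reproduce.

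**2. Recording windows.** Section 8.6.4 records nonserious AEs for 7 days and SAEs for 30 days after the last day in the study.

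| Last day in study | Nonserious AEs to | SAEs to | Visits lost from Day 15 on |
|---|---|---|---|
| Day 71 (as planned) | 71 + 7 = Day 78 | 71 + 30 = Day 101 | none |
| Day 8 | 8 + 7 = Day 15 | 8 + 30 = Day 38 | 15, 29, 43, 57, 71 |
| Day 1 | 1 + 7 = Day 8 | 1 + 30 = Day 31 | 15, 29, 43, 57, 71 |

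The post-dose ADA/nAb endpoint days are 29, 57 and 71. Withdrawal on Day 1 or Day 8 loses all three.

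**3. PK of an active participant.** Under mono-exponential decline, the share of AUC0-inf beyond the last sample at time t is 0.5^(t / half-life). Section 4.2 gives half-lives of 9.4 to 13.6 days, from mice. The limits are 20% (protocol Table 5) and 30% (SAP Table 5).

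| Last sample | t | Half-life 9.4 d | Half-life 13.6 d |
|---|---|---|---|
| Day 8 | 170 h = 7.08 d | 59% | 70% |
| Day 15 | 338 h = 14.08 d | 35% | 49% |
| Day 29 | 674 h = 28.08 d | 13% | 24% |
| Day 71 | 1682 h = 70.08 d | 0.6% | 2.8% |

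With the last sample on Day 8 or Day 15, both limits are exceeded across the range. AUC0-inf, CL, Vz and MRT would then usually leave the SAP summaries. At Day 29 the share is below the SAP limit, but at the longer half-life it exceeds the protocol limit. Cmax, CT and tmax are kept.

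**4. Share of the cohort.** 1/9 = 11% of active participants at a dose; 1/18 = 5.6% of all active participants.

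**5. What still applies after withdrawal.**

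- Section 7.1: "Participants who are withdrawn from the study after interruption or premature discontinuation of study treatment dosing should undergo EOS procedures". This is stated only for that situation.
- Section 8.2.5: clinically significant abnormal laboratory values are repeated.
- Section 8.4: one ADA sample at the final visit.
- Sections 8.6.4 and 8.6.5: events already reported are followed up.
- Schedule of Assessments, footnote m: a PK/ADA/nAb sample for a related SAE.

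None of these restores the remaining scheduled visits.

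**6. Replacement.** Footnote i labels Day 8 as Week 2, so mandatory replacement after withdrawal concerns the days before that. It restores the count of 9 but not the data of the person who had the event. Staff who know the withdrawn participant's assignment could infer the replacement's.

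**The case against.** The strongest case on the other side is that the rule is narrow, rarely invoked and partly mitigated. Much of that stands, and it rules out several stronger readings that a reader might infer.

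- **That every serious or severe event ends follow-up.** The text does not say this. Sponsor unblinding under Section 4.1.2.2 does not by itself trigger the rule. Section 4.1.1 does not say who receives the code, so it triggers the rule only if CRU staff learn the assignment. A severe event need not make the assignment necessary for care.
- **That Section 7.1 flatly contradicts 6.3.1.** Section 7.1 sets a default and itself foresees that some participants are withdrawn. Section 6.3.1 can be read as an exception. This is tension, not direct contradiction.
- **That all safety follow-up stops.** The provisions in step 5 say otherwise, and data collected before withdrawal stay in the Safety Set.
- **That the rule covers everyone because the pharmacist is unblinded.** Section 6.3 provides by design that a "third-party unblinded CRU staff member (eg, pharmacist) will be responsible for the preparation and dispensing". In a section on unblinding, the sentence more naturally means a break of the blind.
- **That replacement triggers the rule again.** Inferring the assignment is possible, but the documents do not say that inference counts as unblinding.

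Two further points are fair. Causality judged after unblinding is no longer blind, so withdrawal is not wholly without purpose. Section 6.3.1 also defers to an Unblinding Plan that is not among the documents; it is described as covering cohort safety review, escalation and stopping rules, and whether it addresses retention is unknown. What the objection does not supply is any provision in the protocol or SAP that keeps an unblinded participant in scheduled follow-up.

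**Conclusion.** The point holds in this limited form and should be fixed. When CRU personnel are unblinded for a participant's medical care, Section 6.3.1 ends that person's scheduled assessments, and the loss is informative. Its size is one participant at a time, 11% of the active group at a dose. The cost is the remaining visits to Day 71, all post-dose ADA/nAb endpoint days after early withdrawal, and usually AUC0-inf, CL, Vz and MRT if the last sample is Day 8 or Day 15.

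The PK shares are illustrative: they rest on mouse half-lives and a one-compartment approximation, and the SAP leaves exclusion open to the PK scientist's judgment. The documents give no probability of unblinding at the CRU, so no expected number of losses can be stated. The study is descriptive and no hypothesis test is affected.

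**What to change.** Reconcile Section 6.3.1 with Sections 7.1 and 7.2:

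- In 6.3.1, delete the clause that withdraws the participant from the study. State that an unblinded participant who consents stays for all remaining scheduled assessments through Day 71.
- Flag assessments made after unblinding in the listings, using the date and reason that 6.3.1 already has recorded.
- In 5.5, state that unblinding alone is not a reason for replacement.

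Whether an infusion in progress is stopped is left to the sponsor and is not part of this change.

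The cost is wording in two sections and one flag, with no added participants and no visits or samples beyond the existing schedule. The small downside is that AE causality assessed after unblinding is not blinded; the flag makes this visible. The gain is a complete profile: with sampling to Hour 1682 the extrapolated AUC share is about 0.6% to 2.8% on the same approximation, and AE and SAE recording runs to Days 78 and 101.
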